3. STUDY DESIGN

3.1 Description of the Study

This is a prospective *between and within group* observational study to determine differences in tolerability, immunogenicity and safety related outcomes for MS patients who have been administered at least two infusions of rituximab, with the last dose of rituximab within 12 months of screening and are willing to be switched to ocrelizumab, compared to patients who are continuing on rituximab as a comparison cohort from the clinic population treated as part of routine clinical care in our program.

The comparator arm is an observational arm only. In addition to prospective data collection, we will collect infusion-related reaction data retrospectively for infusions done after August 1, 2016 (when we began collecting infusion reactions in a standardized way as part of standard of care at the infusion center).

Retrospective data will be collected only after consent is obtained.

In a prospective evaluation with patients at RMMSC who are currently on sustained rituximab treatment for their MS, we will examine the frequency and

severity of IRRs for 100 patients who switch to ocrelizumab (**switching group**) compared to 200 patients continuing rituximab as our primary outcome (**comparator group**). Our secondary outcome is to examine anti-drug antibody formation post switching from rituximab to ocrelizumab (**switching group**). Comparisons for the both outcomes will also be made to findings from the OPERA I and II randomized clinical trials. Other exploratory outcomes including the measurement of B cell reconstitution, cytokine reactions and adverse event profiles will also be examined.

For patients who are switching to ocrelizumab, the first dose of ocrelizumab will be a split dose of 300 mg on day 1 and day 15 followed by 600 mg, six months later as approved by the FDA. The timing of 12 month dose may be delayed due to vagaries in the approval of biologics by third payors. Therefore, we will include data from patients at the T3 visit between the month 12 and 18 after starting ocrelizumab. Standard of care rituximab doses are 1000 mg given as first dose followed by 500mg (or 1000 mg if evidence of early B cell recovery) every 6 months thereafter. Study patients will be current patients of the RMMSC who meet the inclusion criteria and are currently receiving rituximab infusions from the University of Colorado Hospital's Outpatient Infusion Center. Analysis of IRRs will be conducted by the research team at RMMSC. Anti-drug antibody analysis will be conducted by two external vendors: PPD Bio A Laboratories, Richmond, VA will conduct the anti-drug antibodies assays for ocrelizumab, QPS Netherlands, Netherlands will conduct the anti-drug antibodies assays for rituximab using cryopreserved blood samples sent by the RMMSC research team as a single batch at the end of the study. Cytokine analysis will be conducted by personnel at the biobank repository at RMMSC. Study duration, including the recruitment (estimated to take 6 months), data analysis and manuscript development is anticipated to be 24 months.

The study design is represented in **Figure 1** below and described in further detail in section 4.5.1

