1. INTRODUCTION

Studies of rituximab, a chimeric monoclonal antibody against CD20 have shown that B-cell depletion is of significant clinical benefit as a treatment of relapsing forms of multiple sclerosis (MS).¹ Ocrelizumab is a humanized monoclonal antibody that targets CD20 and selectively depletes CD20 expressing cells, while preserving the capacity for B cell reconstitution. When compared with rituximab, ocrelizumab is associated with increased antibody-dependent cell-mediated cytotoxic effects, and reduced complement-dependent cytotoxic effects in vitro.² By increasing antibody-dependent cell mediated cytotoxic effects, ocrelizumab might modulate tissue-dependent mechanisms of pathogenic response more effectively compared to rituximab. As a humanized molecule, ocrelizumab is expected to be less immunogenic with repeated infusions and might thus present a more favorable safety profile when compared to rituximab.²

Despite rituximab's current off label use in the treatment of MS, currently there is only data available from phase 2 trials and open label trials. The HERMES group conducted a phase 2, double-blind, 48-week trial involving 104 patients with relapsing forms of MS; 69 patients received 1000 mg of intravenous rituximab and 35 patients received placebo on days 1 and 15.³ A significantly higher number of patients in the rituximab group (78.3%) versus the placebo group (40.0%) had an infusion related reaction (IRR) events within 24 hours after the first infusion. Within 24 hours after the second infusion, fewer patients in the rituximab group (20.3%) than in the placebo group (40%) had similar events. A majority of the rituximab group with IRR events (92.6%) were classified as mild to moderate (grade 1 or 2) in severity.

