Finally, IRRs have been hypothesized to be a reaction by autoantibodies to the treatment drug or possibly from the release of cytokines from CD20 expressing cells as they are destroyed by ocrelizumab causing a “cytokine storm”. Understanding this process may lead to mechanisms that may aid in ameliorating these infusion reactions. If they are associated with ADA, then it might be possible to predictively premedicate these patients only. Alternatively, if they are associated with cytokine release, it may be possible to eliminate premedication in patients who are already CD20⁺ cell depleted in subsequent infusions. Therefore, we will assay the profile of certain cytokines in the serum 4 hours after start of ocrelizumab infusion.

Since ocrelizumab has entered the market, third party payers within and outside the US have required that the FDA or EMA approved versions of anti-CD20 monoclonal antibodies be used in the treatment of MS, namely ocrelizumab. Currently, we estimate several thousand MS patients in the US and Sweden are taking rituximab currently. Thus, it will be important to demonstrate that switching from a chimeric anti-CD20 to a more fully humanized anti-CD20 does not lead to unexpected infusion reactions and does not increase the probability of development of anti-drug antibodies.

The Rocky Mountain MS Center (RMMSC) at the University of Colorado Anschutz Medical Campus prescribed rituximab infusions for 533 MS patients in the last 12 months, of which 323 patients received their infusion at the University of Colorado Hospital's Outpatient Infusion Center between September, 2015-March, 2016. The RMMSC is one of the few sites nationwide with large numbers of MS patients treated with rituximab. On March 28, 2017, Ocrevus (ocrelizumab) was approved by the FDA for the treatment of primary progressive and relapsing multiple sclerosis. With the approval of ocrelizumab, current rituximab users are being counselled by their MS providers at RMMSC to consider switching to ocrelizumab if it is the only anti-CD20 MAB covered by their insurance.

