4.1.2 Inclusion Criteria

Switching group:

- Current active patient of RMMSC
- 18-65 years
- Diagnosis of relapsing forms of MS
- Completed **≥ two doses** of rituximab with the last dose having been administered:
 - a) within 12 months of screening
 - and
 - b) at least 6 months prior to first planned infusion of study drug
- Are receiving their current infusions of rituximab at the University of Colorado Outpatient Infusion Center
- Have discussed the possibility of switching to ocrelizumab with their MS provider
- Screened for Hepatitis B and C and TB within 2 years of first dose of ocrelizumab
- A negative serum pregnancy test must be available for premenopausal women and for women <12 months after the onset of menopause, unless they have undergone surgical sterilization.
- Women of childbearing potential must agree to use a “highly effective”, hormonal form of contraception or two “effective” forms of non-hormonal contraception. Contraception must continue for the duration of study treatment and for at least three months after the last dose of study treatment
- Are able to complete patient reported outcomes developed as English written scales.
- Must be able and willing to give meaningful, written informed consent prior to participation in the trial, in accordance with local regulatory requirements

Comparator group:

- Current active patient of RMMSC

- 18-65 years
- Diagnosis of relapsing forms of MS
- Completed \geq **two doses** of rituximab with the last dose having been administered within 12 months of screening as standard of care
- Are receiving their current infusions of rituximab as standard of care at the University of Colorado Outpatient Infusion Center and will continue to do so
- Are willing to be followed for subsequent rituximab infusions during the study period as standard of care, and/or allow retrospective data collection on previous rituximab infusions
- Must be able and willing to give meaningful, written informed consent prior to participation in the trial, in accordance with local regulatory requirements

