Potential study patients will be identified from RMMSC electronic medical records (EPIC) using the study inclusion and exclusion criteria. Patients will be recruited by the study coordinator through the University of Colorado's Outpatient Infusion Center. Potential patients are already being identified through their MS providers at RMMSC with whom discussions about the possibility of switching to ocrelizumab are currently underway. Study participants who complete the observation phase of the study will be offered the ability to continue to receive ocrelizumab infusions provided for free by Genentech until ocrelizumab is approved and available to them through their health insurance plan. Once ocrelizumab is available by prescription they will receive priority for assistance through the Genentech/Roche Patient Assistance Program for Ocrelizumab for out of pocket expenses. Ocrelizumab will be provided through priority placement in Genentech's patient assistance program for those patients who are not able to receive insurance coverage for it.

MS patients included in this study will have made a decision with their provider to either stay on rituximab or to switch to ocrelizumab outside of this study. The decision to switch to ocrelizumab or to stay on rituximab will be made as part of

the clinical treatment process between the patient and his/her provider based on his/her disease severity and suitability for treatment among other factors. Therefore, patients are not randomized into either treatment arm. For the group that stays on rituximab, participation in this study is purely observational. For those patients in the rituximab arm who are deemed to be appropriate candidates for switching to ocrelizumab, the option to do so will be provided as standard of care under priority access and/or patient assistance programs (contingent on their individual health insurance status).

It is important to note that because the incidence of IRRs for infusions prior to enrollment are not collected prospectively for those continuing treatment with rituximab and because adverse events including IRRs will not be collected using the same methods for each treatment group following enrollment, interpretation of any difference in the incidence of these events will be limited.

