4.5.1 Assessments during Treatment

The following evaluations will be conducted during and post treatment:

Study Visits and Procedures Summary:

Study visits for the switching group include a) screening visit, b) first infusion of 300 mg of ocrelizumab (day 1 or T₀), c) 300 mg of ocrelizumab infusion on day 15 (T₁), d) 600 mg of ocrelizumab at 6 months (+/- 2 weeks) after day 1 (T₂) and, e) a research termination visit between month 12 and 18 - (+/- 2 weeks)(T₃). In some cases, screening procedures may be performed on the first infusion day rather than as a separate visit. The patient may continue on 600 mg of ocrelizumab or (if the patient prefers) 500mg rituximab at T₃, or 12 to 18 months after Day 1 (T₀). A month is defined as 28 days. Study visits for the comparator group include only standard of care infusion of rituximab, up to two infusions per patient, approximately 6 months apart. Research data on IRRs for the comparator group will be collected from the medical records.

A summary of all procedures for switching group is outlined under “Schedule of Events” in **Table 1** below. During the screening visit, patients will be consented for the study and receive both a medical and full neurological exam. Verification of their hepatitis B and C status including testing will be conducted if a patient has not been tested in the last two years. MS disease history and demographic information will also be collected. Patients will also receive an EDSS exam and take an online version of the PDDS (done as standard of care- on an iPad).

The Expanded Disability Status Scale (EDSS) is a commonly used assessment that allows clinicians to objectively measure changes in the disability status of MS patients using unbiased clinical raters.⁷ The **EDSS** provides a total score on a scale that ranges from 0 to 10. The first levels 1.0 to 4.5 refer to people with a high degree of ambulatory ability and the subsequent levels 5.0 to 9.5 refer to the loss of ambulatory ability. The range of main categories include (0) = *normal neurologic exam*; to (5) = *ambulatory without aid or rest for 200 meters; disability severe enough to impair full daily activities*; to (10) = *death due to MS*. In addition, it also provides seven subscale measurements called Functional System (FS) scores.

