(generalized linear mixed models) methods to incorporate correlation on repeated infusions on a patient. The same method will apply to other longitudinal binary outcomes. Poisson or negative binomial models with exposure terms could calculate rates of IRR per infusion per patient as a counting process. Similar methods will be used to compare IRR rates between the switching group and OPERA I and II phase 3 clinical trials. The total number of IRRs experienced in each patient, will be analyzed with Poisson or negative binomial models. Paired T tests will be used to assess differences in specific cytokine markers between pre and post infusion at each infusion cycle. Patient reported outcomes will also be reported descriptively. Frequencies and proportions will be reported for adverse and serious events and loss to follow up

As contingency methodology, exact tests and confidence intervals for measures of association between categorical variables can be utilized when necessary, if the sample sizes for some of the cells are small. Transforms or rank based methods, such as Wilcoxon sign rank, can be used in place of the T-test if deviation for normality is severe. Otherwise the T-test is a robust test of mean differences for medium to large sample sizes. If matching leads to good balance between the treatment groups on the demographic and disease variables, including age, MS disease duration, and baseline PDDS score, then confounding will not be an issue and the proposed unadjusted tests should be adequate. Alternatively, if the demographic and disease variables are not balanced, then regression or propensity score methods will be used to adjust for potential confounding. Sensitivity analysis comparing unadjusted and adjusted results will be used to determine the extent of the confounding effect. Adjustment for covariates can sometimes improve the precision of the estimated treatment difference by reducing random noise in the outcome.

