the incidence of an IRR for most monoclonal antibodies is highest with the first infusion and declines with subsequent infusions, we recommend that you revise your sample size and power calculations using the IRR incidence for a comparable number of infusions; for example, the first, second, or third infusion”:

Our response is that neither the switching and comparison groups are receiving their very first infusion of any anti-CD 20 monoclonal antibody (rituximab or ocrelizumab) following enrollment in the study. Both study groups have received a minimum of at least two infusions of rituximab prior to enrollment in the study. The first study related infusion for ocrelizumab in the switching group represents (at minimum) their third infusion for an anti-CD monoclonal antibody which will be compared to their third standard of care infusion for rituximab (at minimum) following study enrollment. As a result, we believe both groups represent those patients who have experienced at least three infusions of an anti-CD monoclonal antibody agent. Thereby our power calculations were based on the IRRs observed following the third infusion of rituximab in our pilot sample (at 14.3%) and using a clinically meaningful difference of 20% increase in IRRs for the ocrelizumab group (34.3%) to provide 90% power for 95 patients per study group (assuming a 5% attrition rate after recruiting 100 patients in each study group).

As there is only one primary outcome to power the study on, there is no need to reduce the alpha level of the univariate test as part of multiple testing adjustment. Adjustment for interim analysis is not an issue as there are no early stopping rules.

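### Comparator infusions have no minimum infusion number, so first and second rituximab infusions can enter the primary comparison and mask an ocrelizumab excess

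*Combined protocol and SAP*

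**What the plan says.** Section 3.1 supplements prospective comparator data: "we will collect infusion-related reaction data retrospectively for infusions done after August 1, 2016". Consent is required first. Nothing is said about which infusion in a patient's rituximab course qualifies.

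Section 4.1.2 requires at least two completed rituximab doses at screening. It lets a comparator be followed prospectively and/or "allow retrospective data collection on previous rituximab infusions", so retrospective-only participation is allowed. Section 4.5.1 describes comparator study visits as "up to two infusions per patient, approximately 6 months apart", without saying which two.

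The primary endpoint in section 3.3.1 is the proportion of infusions with at least one IRR. Section 4.9.4 analyses it on available cases. Neither excludes or adjusts by infusion number.

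Section 4.9.6 takes its 14.3% rituximab rate from third infusions in a local chart review. Its reply to the FDA says that the first ocrelizumab infusion "will be compared to their third standard of care infusion for rituximab (at minimum) following study enrollment".

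**The concern.** The FDA comment reproduced in section 4.9.6 is that IRR incidence is usually highest at the first infusion of a monoclonal antibody and then falls, so the groups should be compared at similar infusion numbers. The reply rests on every patient having had two rituximab infusions before enrollment. That is true of the patient on the day of enrollment. It is not true of the earlier infusions that section 3.1 then collects, and an infusion given before enrollment cannot be one that follows it.

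The scenario is feasible. Rituximab is described as given about every six months, so infusions one and two fit the spacing in section 4.5.1. The Introduction already reports the approval of 28 March 2017, nearly eight months after the window opened. A patient who started in August 2016 could have had two doses by then, both inside the window.

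The bias runs in one direction. Every switching patient has at least two prior rituximab doses, so only the comparator arm can contain anti-CD20-naive infusions. These raise the comparator rate and move the result towards concluding that switching is no worse.

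The plan's safeguards do not name infusion number. Matching is on gender and age. The covariate list in section 4.2 is open-ended but leaves infusion number out. Section 4.9.4 says that if matching balances the demographic and disease variables "then confounding will not be an issue and the proposed unadjusted tests should be adequate".

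**Working it through.** **Inputs from the documents**
- Planning rates: 14.3% rituximab (third infusion, local chart review) and 34.3% ocrelizumab; two-sided alpha 0.05; 95 patients per group; stated power 90% (section 4.9.6).
- Planned infusions: 300 ocrelizumab and 200 rituximab, from at least 100 patients per group (section 4.9.6).
- Phase 2 rituximab trial: in the "rituximab group (78.3%) versus the placebo group (40.0%) had an infusion related reaction (IRR) events within 24 hours after the first infusion"; at the second infusion the rituximab rate was 20.3% (Introduction).

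**Assumptions**
- *f*, the share of comparator infusions that are first infusions, is not in the documents. Values of 5% and 10% are used. With 200 infusions from 100 patients and one first infusion per new starter, these mean 10 and 20 new starters.
- *r1*, the local first-infusion rate, is not given. The range is 40% (assumed) to 78.3% (phase 2 trial).
- The ocrelizumab rate stays at 34.3%.

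**Step 1: reproduce the stated power.** For a two-proportion test with pooled variance under the null, power = Φ[(d − 1.96·s0)/s1]. Here d = 0.343 − 0.143 = 0.200. The mean rate is 0.243, so s0 = √(2 × 0.243 × 0.757/95) = 0.0622. Also s1 = √((0.143 × 0.857 + 0.343 × 0.657)/95) = 0.0605. Power is 90.1%, which agrees with the stated 90%.

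**Step 2: comparator rate when first infusions enter.** Rate = (1 − f) × 14.3% + f × r1. For example, with f = 0.05 and r1 = 78.3%: 0.95 × 14.3% + 0.05 × 78.3% = 17.5%.

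**Step 3: power at that rate.** The patient-level column repeats the plan's calculation with 95 per group. The infusion-level column is a rough approximation to the per-infusion GEE/GLMM. It uses effective sizes 300/(1 + 2ρ) and 200/(1 + ρ), with an assumed within-patient correlation ρ of 0.2 to 0.5.

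| f | r1 | Comparator rate | Shift (points) | Power, 95 per group | Power, infusion level (ρ = 0.2 to 0.5) |
|---|---|---|---|---|---|
| 0 | – | 14.3% | 0 | 90.1% | 99.6% to 97.8% |
| 5% | 40% | 15.6% | +1.3 | 85.2% | 98.9% to 95.7% |
| 5% | 78.3% | 17.5% | +3.2 | 75.7% | 96.3% to 90.0% |
| 10% | 40% | 16.9% | +2.6 | 79.1% | 97.4% to 92.2% |
| 10% | 78.3% | 20.7% | +6.4 | 55.6% | 83.9% to 72.6% |

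**Step 4: second infusions.** A 20% share of second infusions alone gives 0.8 × 14.3% + 0.2 × 20.3% = 15.5% and 85.6% power at 95 per group. If 10 of 100 comparators each give infusions one and two (5% of infusions each), the rate rises by 0.05 × (78.3 − 14.3) + 0.05 × (20.3 − 14.3) = 3.5 points, or 1.6 points with r1 = 40%. Power at 95 per group is then 74.0% or 83.9%. First infusions account for nearly all of the effect.

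**The case against.** The strongest reply is that the plan is silent rather than contradictory. Section 3.1 calls the study a prospective evaluation of patients on sustained rituximab, and no sentence puts retrospective infusions into the primary analysis. Read as prospective-only, section 4.9.6 would be correct, because a patient with two doses at screening next receives a third or later one. This reading does not survive the rest of the text. Section 4.1.2 admits comparators with retrospective data only, and they would then contribute nothing. Section 4.2 limits interpretation of the between-group difference "because the incidence of IRRs for infusions prior to enrollment are not collected prospectively for those continuing treatment with rituximab", which treats those infusions as part of the comparison. That caveat concerns how the data are collected, not infusion order.

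Several points about size do stand:
- The share of first infusions is unknown and may be near zero. Before the window opened, "323 patients received their infusion at the University of Colorado Hospital's Outpatient Infusion Center between September, 2015-March, 2016", so many comparators will be long past their first dose.
- The 78.3% comes from a trial with different dosing and a 24-hour window, whose placebo arm had 40%. Here nurses grade at the end of the infusion. If the local first-infusion rate were only 27.5% (the ocrelizumab Day 1 figure in the Introduction, used as a low bound), 5% and 10% shares would add 0.7 and 1.3 points, with 87.8% and 85.1% power at 95 per group.
- Taken literally, section 4.5.1 limits study visits and may not cap retrospective collection at all.
- The patient-level power figures do not describe the per-infusion analysis, which loses less power.

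None of these points changes the direction of the bias or supplies the missing rule.

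**Conclusion.** The concern holds. As written, first and second rituximab infusions can enter the primary comparison, which is inconsistent with the third-or-later, post-enrollment basis given to the FDA in section 4.9.6. The missing rule and the direction of the bias are certain; the size is not. Under the assumed shares of 5% to 10% and first-infusion rates of 40% to 78.3%, the comparator rate rises by 1.3 to 6.4 points against a 20-point target. That shift is the same whether the analysis is per patient or per infusion. The power loss is not: at infusion level, power stays at 90% or above except with a 10% share at 78.3%. Shares above 10% are unlikely given how many patients were treated at the centre before the window. This should be fixed, because the bias favours the reassuring conclusion and nothing in the plan is certain to remove it.

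**What to change.** 1. In sections 3.1 and 4.1.2, restrict the comparator infusions in the primary analysis, retrospective and prospective alike, to each patient's third or later rituximab infusion. State the same analysis set in section 4.9.4.
2. Record the rituximab infusion number for every comparator infusion.
3. In section 4.9.6, correct the statement that comparator infusions follow enrollment, so that it reflects the use of retrospective infusions.
4. Report the comparison with prospective comparator infusions only as a sensitivity analysis. Adjustment for the number of prior infusions can be a further sensitivity analysis and need not be in the primary model.

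The cost is about one sentence in each place and one data field from medical records already being reviewed. The drawback is that some retrospective infusions are lost, so more comparators may be needed to reach 200 infusions. Section 4.1 already allows up to 200 comparator patients.

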4.2 Method of Treatment Assignment

The study will not be a randomized trial. Patients will not be assigned to the switching group, but rather will be enrolled after a clinical decision has been made with their provider about whether they will continue on rituximab or switch

to ocrelizumab. The following steps will be taken to minimize potential biases in sample selection.

First, in an effort to impose some degree of similarity between the treatment groups, control patients will be matched, either 1:1 or 2:1 depending on the number of control patients, with switching patients on gender and age (+/- 2 years) at recruitment. The demographic information on switching patients will be scanned to find matches for the patients in the non-switching group.

Furthermore, screening of additional patients beyond the 200 required for enrollment in the non-switching group will be also conducted to ensure the best possible matches. Second, baseline statistics will be monitored as patients enter the study, and selection of patients may be modified in order to maintain relative balance between treatment groups (if necessary using measures of disease severity other than age and gender) if we are able to overenroll the number of non-switchers. Third, demographic variables and measures of baseline disease severity, including age, gender, MS disease duration, type of MS at baseline (first infusion in both study groups), along with discontinuations, will be recorded and compared between treatment groups.

All available observations will be used. For continuous variables (age, MS disease duration), by treatment group means, standard deviations, medians, and ranges will be recorded, and differences among treatment groups will be tested for with either with T-test/ANOVA methods or Wilcoxon/Kruskal Wallis tests. For categorical variables (gender, type of MS, disability, discontinuations), frequencies and proportions will be presented, and differences among treatment groups will be tested for using chi-square/Fisher's exact test. Fourth, following these measures, if treatment confounding is found to still be an issue, regression or propensity score methods, with covariates such as age, MS disease duration, and baseline EDSS score will be used post hoc to minimize confounding.

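### The primary reaction comparison between self-selected groups has no planned rituximab baseline for switchers: past rituximab reactions are provided for only in the comparator text

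*Combined protocol and SAP*

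**What the plan says.** Section 3.1 opens a paragraph with "The comparator arm is an observational arm only" and continues in that paragraph: "we will collect infusion-related reaction data retrospectively for infusions done after August 1, 2016". The date is explained as the time "when we began collecting infusion reactions in a standardized way as part of standard of care at the infusion center".

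In Section 4.1.2 the comparator list asks patients to be willing to be followed "and/or allow retrospective data collection on previous rituximab infusions". The switching list has no such item. It does require at least two rituximab doses, the last of them "within 12 months of screening", and that patients "Are receiving their current infusions of rituximab at the University of Colorado Outpatient Infusion Center".

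Table 1 (Section 4.5.1) records switchers' IRRs at T0, T1 and T2, all of which are ocrelizumab infusions. The within-switcher IRR comparisons in Sections 2.1 and 3.3.1 set ocrelizumab infusions against each other. Section 2.2, by contrast, does use the switchers' own rituximab-era sample as the baseline for anti-drug antibodies and B cells.

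On allocation, Section 4.2 states: "Patients will not be assigned to the switching group, but rather will be enrolled after a clinical decision has been made". Matching is on gender and age. The adjustment covariates named in Sections 4.2 and 4.9.4 are age, disease duration and EDSS or PDDS. Prior IRR is not among them.

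Two provisions bear on the other side. Section 4.1 lets a patient contribute rituximab data and later join the switching group, and Section 4.9.4 allows GEE or GLMM for repeated infusions on a patient.

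**The concern.** The clinical question is what happens to a patient's reactions when rituximab is replaced by ocrelizumab. The plan answers it by comparing different patients, who reached their group through a decision made with their provider.

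A patient's own reaction history is a natural candidate predictor of the next reaction. If reaction-prone patients are over-represented among switchers, part of any ocrelizumab excess was already there on rituximab. If they are under-represented, a real excess is understated. The reply to the FDA in Section 4.9.6 treats the groups as comparable because both have had at least two rituximab infusions. The switchers' own rituximab IRR rate would test that directly, and it is not a planned data item.

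The records should exist for most switchers, since they were infused at the same centre that has recorded reactions in a standard way since August 1, 2016.

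**Working it through.** **1. The plan's own figure.** Section 4.9.6 gives 14.3% (rituximab) versus 34.3% (ocrelizumab), 95 per group, two-sided alpha 0.05, power 90%.

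Power = Φ[(d − 1.96·SE0)/SE1], with d = 0.200 and mean rate 0.243.
- SE0 = √(2 × 0.243 × 0.757 / 95) = 0.0622
- SE1 = √((0.143 × 0.857 + 0.343 × 0.657) / 95) = 0.0605
- Power = Φ[(0.200 − 0.1220)/0.0605] = 90.1%

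The stated 90% reproduces.

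**2. Illustration of selection bias with no drug effect.** Assumptions, none of them in the documents: 14.3% of comparators are prior reactors; their share among switchers is k × 14.3%, with k = 1.5 or 2; a prior reactor's risk at the next infusion is r = 30% to 50%. The overall comparator rate is held at 14.3%.
- Risk in non-reactors: s = 0.143(1 − r)/0.857
- Switcher rate: k × 0.143 × r + (1 − k × 0.143) × s

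Example, k = 2 and r = 0.40: s = 0.143 × 0.60/0.857 = 0.100; switcher rate = 0.286 × 0.40 + 0.714 × 0.100 = 18.6%; false difference 4.3 points. The last column is the probability that the 95 versus 95 test rejects, both tails counted.

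| k | r | Switcher rate | False difference | Type I error |
|---|---|---|---|---|
| 1.5 | 0.30 | 15.6% | 1.3 points | 5.7% |
| 1.5 | 0.40 | 16.4% | 2.1 points | 6.9% |
| 1.5 | 0.50 | 17.3% | 3.0 points | 8.7% |
| 2 | 0.30 | 16.9% | 2.6 points | 7.9% |
| 2 | 0.40 | 18.6% | 4.3 points | 12.5% |
| 2 | 0.50 | 20.3% | 6.0 points | 19.1% |

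The target difference is 20 points, so even the worst row is under a third of it.

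**3. What a paired test could do.** Same marginal rates, one infusion of each drug per switcher, and an assumed within-patient correlation φ.
- Both infusions with a reaction: p11 = 0.143 × 0.343 + φ × 0.166, where 0.166 = √(0.143 × 0.857 × 0.343 × 0.657)
- Rituximab only: p10 = 0.143 − p11. Ocrelizumab only: p01 = 0.343 − p11. Discordant share: D = p10 + p01
- McNemar power = Φ[(0.200√n − 1.96√D)/√(D − 0.200²)]

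Example, φ = 0.2 and n = 95: p11 = 0.082, D = 0.321, power = Φ[(1.949 − 1.111)/0.530] = 94.3%.

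| Usable pairs | φ = 0 | 0.1 | 0.2 | 0.3 | 0.4 |
|---|---|---|---|---|---|
| 95 | 89.2% | 91.8% | 94.3% | 96.4% | 98.1% |
| 75 | 80.7% | 84.3% | 87.9% | 91.4% | 94.5% |
| 50 | 62.9% | 67.0% | 71.6% | 76.6% | 82.0% |

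The exact test with 95 pairs gives 86.9% to 98.5%. In step 2, r = 0.30 to 0.50 implies φ = (r − 0.143)/0.857 = 0.18 to 0.42 between rituximab infusions. The range here starts at 0 because correlation across the two drugs may be weaker.

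**4. Are the records there?** Ocrelizumab was approved on March 28, 2017 (Section 1), and the last rituximab dose may be up to 12 months before screening. A switcher screened before August 1, 2017 could therefore have had that dose before standardised recording began. The infusion before it is more likely still to fall outside.

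**The case against.** The restriction to comparators is inferred. It rests on where the sentence stands in Section 3.1, on the two inclusion lists and on Table 1. A reader might conclude that collection in switchers is barred or that the data are thrown away. The documents support neither: no sentence forbids it, Section 5.2 allows adverse events to be taken from medical records, and the records stay in the chart. What stands is that no provision is made for it.

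A reader might also infer that nothing planned could reveal a pre-existing imbalance. That goes too far. Dual enrolment with GEE or GLMM could supply some within-patient information, the covariate list in Section 4.2 is open-ended, Section 4.9.4 plans a comparison of unadjusted and adjusted results, and Section 4.2 warns that interpretation will be limited. But the number of dual enrolees is not stated, no paired contrast is specified, and prior IRR cannot serve as a covariate if it is not collected in switchers.

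The bias may be small. Section 1 gives insurance coverage as a reason for switching, and Section 4.1.3 excludes hypersensitivity to trial medications. On the other hand, Section 3.2 expects claims about IRRs to influence some patients, and Section 4.2 cites suitability for treatment. The documents do not settle the size, which is a reason to measure it.

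Finally, the stated objective is switchers versus continuing patients, and pairing has limits of its own. This stands: the paired analysis should support the between-group comparison and not replace it.

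**Conclusion.** The concern holds as a cheap improvement to a non-randomised comparison. The plan makes no provision for switchers' rituximab IRR history, so the primary contrast lacks both a within-patient baseline and a direct check on reaction-proneness before the switch.

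The false difference of 1.3 to 6.0 points and the type I error of about 6% to 19% are illustrations under an assumed 1.5- to 2-fold enrichment and a 30% to 50% repeat risk. They are not estimates for this trial, and the upper end needs both extremes together.

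A reader might take the paired power as a clear gain in precision. It is not assured: with 95 pairs it is 89% at φ = 0, no better than the planned 90%, and it exceeds that only from φ of about 0.1 with nearly complete records. With 75 pairs it is 81% to 95%, and with 50 it is 63% to 82%. The case for the change rests on control of fixed patient factors, not on power.

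**What to change.** - **Sections 3.1, 4.1.2 and Table 1:** extend the retrospective IRR extraction (infusions after August 1, 2016) to consenting switchers, covering the last rituximab infusion and the one before it where recorded. Add a field for the reason for switching.
- **Section 4.9.4:** leave the primary analysis unchanged. Name prior rituximab IRR as a covariate in the adjusted between-group model.
- **Section 4.9.4, supportive analysis:** prespecify the within-patient change from last rituximab to first ocrelizumab infusion (McNemar, or GEE clustered on patient), and its difference from the change between consecutive infusions in comparators. Repeat both without patients who switched because of a rituximab reaction.
- **Reporting:** give the number of switchers with usable records, and state the limits. Some early-screened switchers' last rituximab infusion may predate August 2016. Pairing does not remove regression to the mean, order effects, differences in how reactions were ascertained (conceded in Section 4.2), or differences in infusion regimen between the drugs.

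The cost is one consent sentence, one extra field, and about 100 to 200 chart entries (one or two infusions for each of 100 switchers) of a kind already being abstracted for comparators.
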